4.1 Primary Endpoints

4.1.1 Arterial and Arteriovenous Subjects

For subjects treated for arterial thrombosis (may include diagnoses such as acute limb ischemia, chronic limb ischemia/chronic limb threatening ischemia, peripheral artery disease, etc.) or arteriovenous (AV graft, AV fistula) thrombosis, all endpoints are descriptive.

For subjects treated for arterial or arteriovenous thrombosis, the primary endpoints are:

- **Clot removal grade** for each JETi-treated target vessel from pre-JETi angiogram to post-JETi angiogram (post-JETi thrombectomy and prior to any adjunctive therapies to treat underlying culprit lesions) per the grades in **Table 1** (vessel basis). The independent imaging core laboratory will be responsible for assessing this endpoint.
- **Composite of JETi-related major adverse events** (MAEs) up to 30 days post-JETi procedure, defined as the following JETi-related events adjudicated by a clinical events committee (CEC) (subject basis) death, major amputation of the treated limb, or major bleeding. Refer to **Appendix II** for definitions of major adverse events.

Table 1. Clot Removal Grade

Grade I	< 50% reduction
Grade II	50- <95% reduction
Grade III	95 - 100% reduction

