4.1.2 Venous Subjects

For this study, lower extremity deep vein thrombosis or deep venous thrombosis is defined as lower extremity venous thrombosis involving the femoral, common femoral, iliac, popliteal, or inferior vena cava (IVC) alone or in combination.

For subjects treated for lower extremity DVT, the primary endpoints are:

- **Percent of treated vessel(s) with $\geq 75\%$ venous thrombus reduction** from pre-JETi venogram to final venogram (post-JETi AND after any/all adjunctive therapies to treat underlying culprit lesions) via modified Marder score (limb basis). The independent imaging core laboratory will be responsible for assessing this endpoint.
If no adjunctive therapies or devices are used after JETi, post-JETi modified Marder score is also final score.
- **Composite of JETi-related major adverse events (MAEs)** up to 30 days post-JETi procedure, defined as the following JETi-related events adjudicated by a clinical events committee (CEC): death, symptomatic pulmonary embolism (PE), major bleeding, or re-thrombosis of JETi-treated vessel(s). Refer to **Appendix II** for definitions of major adverse events.

The effectiveness outcome for subjects treated for venous thrombosis that is not lower extremity DVT as defined in Appendix II (e.g., upper extremity DVT) will be assessed by clot removal grade, as defined in Section 4.1.1.

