4.2.2 Arterial and Arteriovenous Subjects

- Clot removal grade for each JETi-treated target vessel from pre-JETi angiogram to final angiogram (post-JETi thrombectomy and after any/all adjunctive therapies and prior to removal of the vascular sheath) per the grades in **Table 1**.
- Components of the MAE, up to 30 days post-JETi procedure, including device-related death, major amputation of treated limb, and major bleeding up to 30 days as adjudicated by a CEC.
- Ankle Brachial Index (ABI) of treated limb(s) at baseline and 30 days. Note this is applicable to lower extremity arterial subjects only.

- Rutherford classification of treated limb(s) at baseline and 30 days. Note this is applicable to lower extremity arterial subjects only.
- Re-thrombosis of JETi-treated vessel at 30-day follow-up, as assessed by investigator/physician reported.
- Patency as determined by duplex ultrasound at baseline and 30-day. Note that this endpoint will only apply to subjects treated for arteriovenous thrombus.
- **Vessel patency:** assessed by the independent imaging core laboratory using the Modified Thrombolysis in Myocardial Infarction (TIMI) classification called TIPI (Thrombo-aspiration in Peripheral Ischemia)⁵ (**Table 3**) for each JETi-treated vessel, assessed using angiogram
 - At post-JETi timepoint (post-JETi thrombectomy and prior to any adjunctive therapies to treat underlying culprit lesions)
 - At final timepoint (post-JETi thrombectomy and after any/all adjunctive therapies and prior to removal of the vascular sheath)

If no adjunctive therapies or devices are used after JETi, post-JETi TIPI score is also final TIPI score.

Table 3. Thrombo-aspiration in Peripheral Ischemia (TIPI)

Description	TIPI score
No recanalization of the thrombotic occlusion	0
Incomplete or partial recanalization of the thrombotic occlusion with no distal flow	1
Incomplete or partial recanalization of the thrombotic occlusion with any distal flow	2
Complete recanalization of the thrombotic occlusion with normal distal flow	3

- Acute success, as per [REDACTED] (**Table 3**):
 - Device success: Near complete or complete recanalization of occluded vessel, defined as post-JETi [REDACTED]
 - Technical success: Near complete or complete recanalization of occluded vessel, defined as final [REDACTED] where [REDACTED] evaluation occurs after JETi system and any other adjunctive device or procedures.

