4.2.3 Venous Subjects

- Percent of treated vessels (in lower extremity DVT) with $\geq 75\%$ thrombus reduction from pre-JETi venogram to post-JETi venogram (post-JETi thrombectomy and before any adjunctive therapies to treat underlying culprit lesions) via modified Marder score. The independent imaging core laboratory will be responsible for assessing this endpoint. Note this is applicable to lower

⁵ de Donato G, Pasqui E, Sponza M, et al. Safety and Efficacy of Vacuum Assisted Thrombo-Aspiration in Patients with Acute Lower Limb Ischaemia: The INDIAN Trial. *Eur J Vasc Endovasc Surg.* 2021;61(5):820-828. doi:10.1016/j.ejvs.2021.01.004

extremity DVT subjects only. The effectiveness outcome for subjects treated for venous thrombosis that is not lower extremity DVT as defined in Appendix II (e.g., upper extremity DVT) will be assessed by clot removal grade, as defined in Section 4.1.1.

- Components of the MAE up to 30 days post-JETi procedure, including the following JETi-related events adjudicated by a CEC: device-related death, symptomatic pulmonary embolism (PE), major bleeding, and re-thrombosis of JETi treated vessel(s).
- The Villalta Post Thrombotic Syndrome (PTS) severity scale at baseline, and 30-day follow-up. Note this is applicable to lower extremity DVT subjects only.
 - Edema component score from the Villalta Post Thrombotic Syndrome (PTS) severity scale at baseline, and 30-day follow-up.
- A 7-point Likert Scale for leg pain at baseline, discharge, and 30-day follow-up. Note this is applicable to lower extremity DVT subjects only.
- Venous patency and compressibility as determined by duplex ultrasound at baseline, and 30-day follow-up. The independent imaging core laboratory will be responsible for assessing this endpoint.
- Acute success, [REDACTED], assessed by core laboratory:

- Device success: post-JETi thrombus removal grade II-III [REDACTED]
 - Technical success: Final thrombus removal grade II-III, [REDACTED] where final [REDACTED] evaluation occurs after JETi system and any other adjunctive device or procedures.
- Procedural success: Technical success with no JETi-related MAEs within 5 days of registration or by discharge, whichever occurs first.

If no adjunctive therapies or devices are used after JETi, post-JETi [REDACTED] score is also final [REDACTED] score.

[REDACTED]		[REDACTED]		[REDACTED]	

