7.2 Device Relationship

Determination of whether there is a reasonable possibility that the JETi System caused or contributed to an AE is to be **determined by the Investigator** and recorded on the appropriate case report (CRF) form. Determination should be based on the assessment of temporal relationships, evidence of alternative etiology, medical/biologic plausibility and patient condition (pre-existing condition).

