7.3 Adverse Event and Device Deficiency/Device Malfunction Reporting

7.3.1 Adverse Event Reporting

Safety surveillance and reporting starts as soon as the JETi catheter is introduced into the intended vasculature during the procedure. Safety surveillance and reporting will continue until sites perform the last follow-up visit, the subject is deceased, the subject concludes participation in the clinical investigation, or the subject withdraws from the clinical investigation. Sites will collect all adverse event data, including deaths and device deficiency data (if applicable), throughout the period defined above, and will report these events to the Sponsor on a CRF. Sites should update additional information regarding an adverse event on the appropriate CRF.

Unchanged, chronic, non-worsening or pre-existing conditions are not AEs and should not be reported.

The Sponsor will provide an offline form to allow the investigator to report SAEs in the event the entry cannot be made in the electronic data capture (EDC). This does not replace the EDC reporting system. Sites must still enter all information in the EDC system as soon as feasible.

For the purposes of this study, the following adverse events will be reported for each subject through the 30-day follow-up visit.

- All device-and procedure-related AEs
- All SAEs

In addition, the following adverse events regardless of seriousness or relatedness will be collected:

[REDACTED]
[REDACTED]
[REDACTED]
[REDACTED]
[REDACTED]
[REDACTED]
[REDACTED]
[REDACTED]

SAE Reporting

The investigator must report all SAEs to the Sponsor as soon as possible but no later than outlined below.

Clinical Site	Reporting timelines
All Sites	Sites must report SAEs to the Sponsor no later than 3 calendar days from the day the site personnel became aware of the event or as per the investigative site's local requirements, if the requirement is more stringent than those outlined.

Sites must record the date the site staff became aware that the event met the criteria of an SAE in the source document. The Investigator will further report the SAE to the local IRB/EC according to the institution's IRB/EC reporting requirements.

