8.2.1 Primary Endpoints Analyses

The primary endpoints are:

Arterial and Arteriovenous subjects

For subjects treated for lower extremity arterial thrombosis, the primary endpoints are:

- **Clot removal grade** for each JETi-treated target vessel from pre-JETi angiogram to post-JETi angiogram (post-JETi thrombectomy and prior to any adjunctive therapies to treat underlying culprit lesions) per the grades in **Table 1** (vessel basis). The independent imaging core laboratory will be responsible for assessing this endpoint.
- **Composite of JETi-related major adverse events** (MAEs), defined as the following JETi-related events: device-related death, major amputation of the treated limb (arterial subjects only), or major bleeding up to 30 days post registration and as adjudicated by a clinical events committee (CEC) (subject basis). Refer to Appendix II for definitions of major adverse events.

Table 7. Clot Removal Grade

Grade I	< 50% reduction
Grade II	50- <95% reduction
Grade III	95 - 100% reduction

Venous Subjects

For this study, lower extremity deep vein thrombosis or deep venous thrombosis is defined as lower extremity venous thrombosis involving the femoral, common femoral, iliac, popliteal, or inferior vena cava (IVC) alone or in combination.

For subjects treated for lower extremity DVT, the primary endpoints are:

- **Percent of treated vessel(s) with $\geq 75\%$ venous thrombus reduction** from pre-JETi venogram to final venogram (post-JETi AND after any/all adjunctive therapies to treat underlying culprit lesions) via modified Marder score (limb basis). The independent imaging core laboratory will be responsible for assessing this endpoint.

- **Composite of JETi-related major adverse events (MAEs)** up to 30 days post-JETi procedure, defined as the following JETi-related events adjudicated by a clinical events committee (CEC): death, symptomatic pulmonary embolism (PE), major bleeding, or re-thrombosis of JETi-treated vessel(s). Refer to **Appendix II** for definitions of major adverse events.

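### The 30-day safety composites count only JETi-related events, and no endpoint gives an all-cause major adverse event or amputation rate beside them

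*Combined protocol and SAP*

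**What the plan says.** **Primary composites.** For arterial and AV subjects, section 4.1.1 counts "the following JETi-related events adjudicated by a clinical events committee (CEC) (subject basis) death, major amputation of the treated limb, or major bleeding". For lower extremity DVT, section 4.1.2 counts these events if JETi-related: "death, symptomatic pulmonary embolism (PE), major bleeding, or re-thrombosis of JETi-treated vessel(s". Section 8.2.1 repeats both composites, and on the arterial side it restricts death a second time: "device-related death, major amputation of the treated limb (arterial subjects only), or major bleeding up to 30 days post registration". The summary in Appendix XI is also limited to JETi-related events.

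**Component endpoints.** The venous bullet in 4.2.3 is explicit: "including the following JETi-related events adjudicated by a CEC: device-related death, symptomatic pulmonary embolism (PE), major bleeding, and re-thrombosis of JETi treated vessel(s". The arterial/AV bullet in 4.2.2 is not: "including device-related death, major amputation of treated limb, and major bleeding up to 30 days as adjudicated by a CEC". There the qualifier sits on death only.

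**Other safety items.** Section 4.2.1 lists procedure-related death, JETi-related adverse events and procedure-related access site complications. Procedural success (4.2.2, 4.2.3) requires technical success without a JETi-related MAE up to day 5 or discharge, whichever comes first.

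**Relatedness and collection.** Section 7.2 has the investigator weigh temporal relationship together with "evidence of alternative etiology, medical/biologic plausibility and patient condition (pre-existing condition". Section 7.3.1 says "the following adverse events will be reported for each subject through the 30-day follow-up visit", and the list that follows includes all serious adverse events. It also provides for a second, blacked-out list of events collected whatever their seriousness or cause.

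**The concern.** Limb loss is a possible outcome of limb ischemia, and PE and re-thrombosis are possible outcomes of DVT. A relatedness filter on these events asks, case by case, whether the device or the disease was responsible. Section 7.2 names alternative etiology and pre-existing condition among the factors to weigh, and every eligible subject has a pre-existing thrombotic condition. A single-arm study has no comparison group in which a device excess missed by individual attribution could show up.

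The stated objective covers safety, performance and clinical benefit in real-world use. If the headline 30-day figure is a JETi-related rate and nothing beside it counts the same events regardless of cause, a reader cannot tell a cohort with no limb loss from one in which limbs were lost and the losses were attributed to the disease.

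**Working it through.** The plan gives no event rate, power or arterial/venous split, so it has no figure of its own to reproduce. The check is a comparison of wording, followed by arithmetic for scale.

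**Step 1: which results carry a relatedness filter?**

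| Result | Section | Filter |
|---|---|---|
| Arterial/AV composite | 4.1.1, 8.2.1 | JETi-related |
| Venous composite | 4.1.2, 8.2.1 | JETi-related |
| Venous components | 4.2.3 | JETi-related |
| Arterial/AV components | 4.2.2 | death device-related; amputation and bleeding unmarked |
| Procedural success | 4.2.2, 4.2.3 | no JETi-related MAE |
| Death, all subjects | 4.2.1 | procedure-related |
| Arterial/AV re-thrombosis at 30 days | 4.2.2 | none |
| ABI, Rutherford (lower extremity arterial) | 4.2.2 | none |
| AV duplex patency | 4.2.2 | none |
| Venous duplex patency and compressibility | 4.2.3 | none |
| Villalta, leg pain (lower extremity DVT) | 4.2.3 | none |
| SF-12 | 4.2.1 | none |

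No row is expressly an all-cause composite or an all-cause major amputation rate. Symptomatic PE appears only in filtered form. Re-thrombosis has an unfiltered event endpoint for arterial/AV subjects but only a JETi-related one for venous subjects. The visible text of section 8 names no summary of all serious adverse events.

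**Step 2: can the unfiltered rows stand in for an event count?** In part.

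- ABI, Rutherford class, duplex and Villalta record status at baseline and 30 days. A vein that re-thromboses and is retreated before day 30 may be patent at the visit.
- Major amputation is defined in Appendix II as above the ankle, and ABI needs an ankle pressure. ABI for a lost limb would be missing and would be excluded under 8.8.
- The footnotes to both schedules allow a telephone or virtual visit when an office visit is impossible, which also leaves the physical measures missing.

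**Step 3: size.** The number of subjects, about 20, is from 8.3. The stratum sizes and event counts below are assumptions.

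- Points per excluded event: 100 × 1/20 = 5; with 10 subjects, 100 × 1/10 = 10.
- The exact (Clopper-Pearson) 95% limits for x events in n subjects are the 2.5% quantile of Beta(x, n − x + 1) and the 97.5% quantile of Beta(x + 1, n − x). For x = 0 the lower limit is 0 and the upper limit is 1 − 0.025^(1/n); with n = 10 that is 1 − 0.6915 = 30.8%.

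Suppose two events occur and both are judged unrelated to JETi:

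| n | JETi-related result | All-cause result |
|---|---|---|
| 5 | 0% (0 to 52.2%) | 40% (5.3 to 85.3%) |
| 10 | 0% (0 to 30.8%) | 20% (2.5 to 55.6%) |
| 15 | 0% (0 to 21.8%) | 13.3% (1.7 to 40.5%) |
| 20 | 0% (0 to 16.8%) | 10% (1.2 to 31.7%) |

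- The chance that at least one subject has an event that the filter removes is 1 − (1 − p)^n, with p the assumed per-subject probability of an event judged unrelated and subjects independent. For p from 5% to 20% it runs from 40% to 89% with n = 10, and from 64% to 99% with n = 20.

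**The case against.** The strongest reply is that this is a small descriptive study with no hypothesis, that a device-related composite is a legitimate primary endpoint, and that an uncontrolled all-cause rate would not isolate a device effect either. All of that stands, and it is why the primary endpoint should not change. It does not explain why the all-cause count should be absent.

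A reader might also infer several stronger things that the documents do not support:

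- **That every MAE component is filtered.** In 4.2.2 only death carries the qualifier. Amputation and bleeding are JETi-related only by inference from their being components of the MAE.
- **That a disease-driven event leaves all safety and benefit results untouched.** Arterial/AV re-thrombosis is an unfiltered endpoint. A re-thrombosed vein can show in core-laboratory duplex, Villalta, leg pain or SF-12. An amputation should be reported as a serious adverse event and could affect Rutherford class or SF-12.
- **That the filter would remove most such events.** Section 7.2 asks whether there is a reasonable possibility that the device caused or contributed to the event, which is an inclusive threshold, and it governs the investigator's judgment. The composite is adjudicated by the CEC under a charter that is not part of these documents.
- **That mortality is equally exposed.** Appendix II presumes a death within 30 days to be procedure-related unless history or autopsy shows otherwise, and 4.2.1 reports procedure-related death separately. There is no such presumption for amputation, PE or re-thrombosis.
- **That the results could not be compared with published series.** The introduction does not say whether the earlier studies counted events regardless of cause.

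The blacked-out list in 7.3.1 may name some of these events. That would settle their collection but would not make them a planned endpoint.

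**Conclusion.** The point holds for the MAE results and procedural success. Both primary composites, the venous components and procedural success are restricted to JETi-related events; the arterial/AV component wording allows two readings; and nothing visible commits the study to an all-cause 30-day MAE or major amputation rate. An analyst could follow the plan and report 0% MAE in a cohort with disease-attributed limb loss or PE. The unfiltered endpoints and the serious adverse event reports would capture part of this, but apart from arterial/AV re-thrombosis they are status measures or raw reports, not event rates.

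The size cannot be fixed from the documents. The 5 points per event follows from about 20 subjects; the 0/10 against 2/10 contrast and the probabilities rest on assumed counts, rates and strata, and say nothing about what will be observed. This is a worthwhile, inexpensive improvement to reporting and not a reason to replace the primary endpoint.

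**What to change.** 1. Keep the JETi-related composites as primary.
2. State in 4.2.2 whether the amputation and bleeding components are JETi-related or all-cause.
3. In 4.2.2, 4.2.3 and section 8, add descriptive 30-day counts regardless of relatedness, shown beside the JETi-related counts: death and major bleeding for all subjects, major amputation of the treated limb for arterial subjects, and symptomatic PE and re-thrombosis of a treated vessel for venous subjects.
4. Have the CEC confirm first that the event occurred and then whether it was JETi-related, working from the serious adverse events reported under 7.3.1.
5. Align the venous collection text in 6.2 with 7.3.1. Section 6.2 describes a sequence of relatedness judgments that ends in collection of JETi-related events, whereas 7.3.1 requires all serious adverse events through the 30-day visit.

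The cost is protocol and table wording. The downside is that the CEC confirms a few more events, and a less favourable figure may appear beside the primary one.

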4.1.2 Venous Subjects

For this study, lower extremity deep vein thrombosis or deep venous thrombosis is defined as lower extremity venous thrombosis involving the femoral, common femoral, iliac, popliteal, or inferior vena cava (IVC) alone or in combination.

For subjects treated for lower extremity DVT, the primary endpoints are:

- **Percent of treated vessel(s) with $\geq 75\%$ venous thrombus reduction** from pre-JETi venogram to final venogram (post-JETi AND after any/all adjunctive therapies to treat underlying culprit lesions) via modified Marder score (limb basis). The independent imaging core laboratory will be responsible for assessing this endpoint.
If no adjunctive therapies or devices are used after JETi, post-JETi modified Marder score is also final score.
- **Composite of JETi-related major adverse events (MAEs)** up to 30 days post-JETi procedure, defined as the following JETi-related events adjudicated by a clinical events committee (CEC): death, symptomatic pulmonary embolism (PE), major bleeding, or re-thrombosis of JETi-treated vessel(s). Refer to **Appendix II** for definitions of major adverse events.

The effectiveness outcome for subjects treated for venous thrombosis that is not lower extremity DVT as defined in Appendix II (e.g., upper extremity DVT) will be assessed by clot removal grade, as defined in Section 4.1.1.

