5.3.2 Inclusion Criteria

5.3.2.1 General Inclusion Criteria

1. Subject was treated or is expected to be treated for acute/subacute thrombosis, as determined by investigator, in the peripheral vasculature with the JETi Hydrodynamic Thrombectomy System.
2. Subject or legally authorized representative must provide written informed consent
3. Subject must be ≥ 18 years of age and of Asian race.

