APPENDIX X: REVISION HISTORY

APPENDIX XI: CIP SUMMARY

Clinical Investigation Name	JETi Hong Kong Post Market Study
Title	JET Enhanced Thrombectomy intervention Hong Kong Post Market Study
Objective	To collect real-world data on the safety, performance, and clinical benefits of the JETi System for the treatment of thrombosis in the peripheral vasculature
Device	JETi™ Hydrodynamic Thrombectomy System
Number of Subjects	Approximately 20 subjects
Clinical Investigation Design	A single-arm, multi-center study
Primary Endpoint(s)	
For subjects treated for arterial thrombosis:
 
 • Clot removal grade for each JETi-treated target vessel from pre-JETi angiogram/venogram to post-JETi angiogram/venogram (post-JETi thrombectomy and prior to any adjunctive therapies to treat underlying culprit lesions) per the grades in Table 1. The independent imaging core laboratory will be responsible for assessing this endpoint. • Composite of JETi-related major adverse events (MAEs) up to 30 days post-JETi procedure, defined as the following JETi-related events adjudicated by a CEC: death, major amputation of the treated limb (arterial subjects only), or major bleeding. Refer to Appendix II for definitions of major adverse events. 
For subjects treated for venous thrombosis:
 
 • Percent of treated vessel(s) with $\geq 75\%$ venous thrombus reduction from pre-procedure venogram to final venogram (post-JETi AND after any/all adjunctive therapies to treat underlying culprit lesions) via modified Marder score. • Composite of JETi-related major adverse events (MAEs) up to 30 days post-JETi procedure, defined as the following JETi-related events adjudicated by a clinical events committee (CEC): death, symptomatic pulmonary embolism (PE), major bleeding, or re-thrombosis of JETi-treated vessel(s). Refer to Appendix II for definitions of major adverse events.
Subject Follow-up	Office visits at 30 days after the start of JETi procedure (Day 0).
Inclusion Criteria	
 1. Subject was treated or is scheduled to be treated for acute/subacute thrombosis as determined by the investigator in the peripheral vasculature with any of the JETi System. 2. Subject must provide written informed consent. 3. Subject must be ≥ 18 years of age and of Asian race.

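### Sections 4.1.2 and 8.2.1 leave eligible venous subjects without lower extremity DVT out of both primary MAE composites, while Appendix XI includes them

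*Combined protocol and SAP*

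**What the plan says.** **Eligibility.** Section 5.3.2.1 requires that "Subject was treated or is expected to be treated for acute/subacute thrombosis, as determined by investigator, in the peripheral vasculature" with the JETi System. It sets no limit on venous site. The plan expects veins outside the lower extremity: Section 4.1.2 names upper extremity DVT as an example, and Section 6.2.2 has a separate imaging rule for such vessels.

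**Venous primary endpoints.** Section 4.1.2 opens them with "For subjects treated for lower extremity DVT, the primary endpoints are". Two endpoints follow: thrombus reduction by modified Marder score, and the CEC-adjudicated composite of JETi-related death, symptomatic PE, major bleeding or re-thrombosis of treated vessels. Section 8.2.1 uses the same lead-in.

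**Other venous subjects.** Section 4.1.2 closes with a sentence that begins "The effectiveness outcome for subjects treated for venous thrombosis that is not lower extremity DVT as defined in Appendix II" and continues "e.g., upper extremity DVT) will be assessed by clot removal grade, as defined in Section 4.1.1". Section 8.2.1 has no counterpart to it.

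**The other composite.** Section 4.1.1 states "For subjects treated for arterial or arteriovenous thrombosis, the primary endpoints are". Its composite is death, major amputation of the treated limb or major bleeding, on a subject basis.

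**Descriptive endpoints for venous subjects (Section 4.2.3).** One item is "Components of the MAE up to 30 days post-JETi procedure, including the following JETi-related events adjudicated by a CEC: device-related death, symptomatic pulmonary embolism", followed by major bleeding and re-thrombosis. Another is "Procedural success: Technical success with no JETi-related MAEs within 5 days of registration or by discharge, whichever occurs first". Neither is limited to lower extremity DVT, although the Marder, Villalta and leg-pain items in the same list are.

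**Summary.** Appendix XI heads its venous primary endpoints "For subjects treated for venous thrombosis" and lists both the Marder endpoint and the MAE composite beneath, with no site limit.

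**The concern.** The study objective covers safety throughout the peripheral vasculature, and Section 8.1 puts every registered subject in the analysis. A programmer who follows the endpoint and analysis sections would nevertheless give one eligible group an effectiveness result and no primary safety result. Its subjects would be missing from both the numerator and the denominator of the venous composite. A programmer who follows Appendix XI would count them. The two readings give different primary safety rates from the same data.

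There is also a reporting problem inside the venous tables. If components are tabulated over all venous subjects and the composite over lower extremity DVT only, a report could show a symptomatic PE among the components next to a composite count of zero. In a study of about 20 subjects, a discrepancy of one event would be conspicuous.

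**Working it through.** The plan gives no figure to reproduce: there is no hypothesis test, no power statement and no split of the sample by vascular bed. The check is mainly textual.

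**Step 1. Follow one case through the document.** Take a registered subject with upper extremity DVT who has a JETi-related symptomatic PE within 30 days.

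| Place | Population as stated | Is this PE counted? |
|---|---|---|
| 4.1.1 primary composite | Arterial or arteriovenous | No; PE is not a component either |
| 4.1.2 primary composite | Lower extremity DVT | No |
| 8.2.1 primary composite | Lower extremity DVT | No |
| Appendix XI primary composite | All venous thrombosis | Yes |
| 4.2.1 JETi-related AEs | All subjects | Yes, descriptive |
| 4.2.3 MAE components | Venous, no site limit | Yes, descriptive |
| 4.2.3 procedural success | Venous, no site limit | Yes, if within 5 days or by discharge, whichever is first |

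The cross-reference to Section 4.1.1 in the closing sentence of Section 4.1.2 does not bring in the arterial composite. Its subject is the effectiveness outcome, and what it imports is the clot removal grade. The arterial composite would be a poor substitute in any case, since it has neither PE nor re-thrombosis.

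**Step 2. Denominators.** Let V be the number of venous subjects and m the number of them without lower extremity DVT. If the only event is one MAE among the m:

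- component table (4.2.3): 1/V
- composite under 4.1.2 and 8.2.1: 0/(V − m)
- composite under Appendix XI: 1/V

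**Step 3. Direction of the change.** With x events in the V − m lower extremity subjects and y in the other m, including everyone moves the rate from x/(V − m) to (x + y)/V. It rises if y/m exceeds x/(V − m) and falls if y/m is smaller. The direction cannot be known in advance.

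**Step 4. Size, by illustration only.** The documents give N of about 20. The values of m and the MAE risk p are assumptions. The share of registered subjects with no primary safety endpoint under 4.1.2 and 8.2.1 is m/20. The chance that at least one MAE falls outside both composites is 1 − (1 − p)^m.

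| m (assumed) | m/20 | p = 5%: 1 − 0.95^m | p = 10%: 1 − 0.90^m |
|---|---|---|---|
| 1 | 5% | 5.0% | 10.0% |
| 2 | 10% | 9.8% | 19.0% |
| 3 | 15% | 14.3% | 27.1% |
| 4 | 20% | 18.5% | 34.4% |

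The m/20 column describes coverage of registered subjects. It is not a change in any reported rate, because no visible endpoint uses 20 as its denominator: the arterial and venous composites are defined separately, and the pooling text in Section 8.7 is redacted.

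**The case against.** The strongest reply is that the plan means to cover these subjects and that only the lead-in is loose. Three things support it. The closing sentence of Section 4.1.2 substitutes the effectiveness outcome alone, which can be read as leaving safety common to all venous subjects. Section 4.2.3 marks some items as lower extremity only and leaves the MAE items unmarked. Lead-ins elsewhere are also imprecise: in Section 8.2.1 the arterial and arteriovenous block opens with lower extremity arterial thrombosis, yet its composite limits amputation to arterial subjects, which makes sense only if arteriovenous subjects are included.

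This stands as evidence about intent, and a deliberate exclusion is not shown. It does not settle what an analyst should do, because the endpoint section and the analysis section both state the restriction. Appendix XI cannot settle it either. It appears abbreviated, and it also gives the Marder endpoint to all venous subjects, against Sections 4.1.2 and 6.2.2.

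A reader might infer that no part of the document gives these subjects a primary safety endpoint, or that their device-related deaths, PEs and bleeds would go unreported. The documents support neither. Appendix XI gives them the composite. Section 7.3.1 collects all SAEs and all device- and procedure-related AEs. Section 4.2.1 reports CEC-adjudicated JETi-related AEs and procedure-related death in all subjects, and Section 4.2.3 reports the MAE components for venous subjects.

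It is also fair to say that the endpoints are descriptive, so no test or error rate is affected.

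**Conclusion.** The point holds as an inconsistency that changes who counts in the primary safety result. Under Sections 4.1.2 and 8.2.1, JETi-related MAEs in eligible venous subjects without lower extremity DVT enter neither primary composite. Appendix XI says the opposite, and Section 4.2.3 uses a wider population for the components than those sections use for the composite.

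The loss is confined to the primary safety result. How many subjects it affects is unknown: the 5% to 20% range rests on an assumed 1 to 4 such subjects among about 20, and the event probabilities rest in addition on assumed MAE risks of 5% and 10%. If no such subject is registered, nothing changes numerically. Severity is minor to moderate, given a descriptive study of this size.

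**What to change.** - In Sections 4.1.2 and 8.2.1, apply the venous MAE composite to all subjects treated for venous thrombosis.
- State that it is evaluated on a subject basis. This is new wording for the venous composite, which does not now name its unit; it matches Section 4.1.1.
- Keep the modified Marder endpoint for lower extremity DVT and clot removal grade for other venous subjects, and carry the latter rule into Section 8.2.1, which omits it.
- Align Appendix XI, which now gives Marder to all venous subjects.

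The composite in Section 4.1.2 and its components in Section 4.2.3 would then share one population, and every registered subject would fall under one of the two primary composites.

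The cost is a wording amendment, best made before analysis. It needs no added subjects, visits or data, since the events are already collected under Section 7.3.1 and CEC-adjudicated JETi-related AEs are already planned for all subjects in Section 4.2.1. The venous MAE rate may move slightly in either direction.
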